4.2.8.10 Serum benralizumab concentration

The PK analyses will be performed at or under the guidance of AstraZeneca Research and Development. Benralizumab serum concentrations will be summarized using descriptive statistics at each scheduled visit for participants in the PK analysis set.

4.2.8.11 Anti-drug antibodies (ADA)

Anti-drug antibodies to benralizumab will be summarized using descriptive statistics by treatment group and each visit specified in the CSP Table 2. The ADA titres-time profiles of benralizumab may be generated. The impact of ADA on PK and eosinophil level will be assessed. The potential association of ADA with safety and efficacy will be evaluated.

Further details are provided in Appendix [8.2](#).

4.2.9 Safety Analyses

Safety analyses will be performed using the safety analysis set.

Summaries will be presented for the double-blind period and the OLE period. A small number of key tables might also be presented for data in the overall study period including only participants who received benralizumab during the double-blind period.

Participants will be analysed according to the treatment they received. In general, the baseline value for statistical analysis is the last non-missing value prior to administration of the first dose of IP. More details are reported in Section [3.1.1](#).

Safety data will be presented using descriptive statistics. No safety data will be imputed.

4.2.9.1 Adverse Events

Treatment Emergent Adverse Events (TEAEs) will be summarized separately for the on-treatment, on-study, and post-treatment periods, as defined in Section [3.5.1](#). The primary period of interest for safety summaries will be the on-treatment period, unless differently specified.

Adverse events in the pre-treatment period (with start date prior to the first dose of IP) will be listed for the double-blind treatment period at primary database lock only.

Non-serious AEs with an onset date after the on-treatment period will be listed but excluded from the summaries.

All summaries will be presented by treatment group and key tables will include exposure-adjusted rates to account for any differences in follow-up if applicable.

An overall summary table will be produced showing the number, percentage, and exposure-adjusted rate of participants with at least 1 TEAE in any of the following categories; TEAEs, SAEs, AEs with outcome of death, and AEs leading to discontinuation of IP (DAEs).

The rate of TEAEs, SAEs, AEs with outcome of death and DAEs per person-years at risk will be calculated for the on-treatment period as (number of participants reporting the TEAE) / (total time with participants at risk of TEAE). For SAEs and AEs with outcome of death the rate per person-years at risk will be calculated also for the on-study period as (number of participants reporting the TEAE) / (total time with participants at risk of TEAE). The total period at risk for each participant will be the duration of the on-treatment and on-study periods as defined in Section 3.5.1. Rates will be expressed in terms of events per 100 participant-years.

The post-treatment AEs will be listed.

Treatment-emergent AEs, AEs with outcome of death, SAEs and DAEs will be presented for each treatment group for the on-treatment and on study periods by SOC and PT, including the number and percentage of participants reporting at least one event (ie, multiple occurrences of an AE for a participant will only be counted once), number of events and exposure-adjusted rates (where applicable).

A summary of the most common (frequency of >5%) TEAEs will be presented by PT.

Treatment-emergent AEs and SAEs causing discontinuation of the study treatment and SAEs causing discontinuation from the study will also be summarized.

Treatment-emergent AEs, SAEs and DAEs will be summarized by preferred term and Investigator's causality assessment (related versus not related) and maximum intensity, including reporting of seriousness, death and events leading to discontinuation of IP, as well as other action taken related to IP.

If a participant reports multiple occurrences of the same TEAE within the same study period, the worst-case Investigator's causality assessment (the order being not related and related) will be taken as Investigator's causality assessment and the highest recorded maximum intensity (the order being mild, moderate, and severe) will be taken as intensity.

Other significant TEAEs will include but may not be limited to injection site reactions and hypersensitivity events. Treatment-emergent AEs of injection site reactions (high level term of injection site reactions) and hypersensitivity (standardized MedDRA query of hypersensitivity [narrow]) will be summarized by preferred term. The injection site reactions will be summarized by injection site location and number of IP administrations. The summary of TEAEs of hypersensitivity will be presented overall and repeated for events causally related to IP as assessed by the Investigator. Hypersensitivity events will be listed.

Key participant information will be presented for participants with AEs with outcome of death, SAEs, and DAEs.

Separate listings of participants with AEs, AEs with outcome of death, SAEs, or DAEs will be presented.

Adverse events ongoing at primary DBL will be presented for both primary and final DBL reporting.

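### The exposure-adjusted AE rate counts participants over full follow-up but is labelled as events, so it is neither an event rate nor a first-event incidence rate

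*SAP*

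**What the plan says.** SAP 4.2.9.1 (Adverse Events) makes four statements that have to be read together.

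- **Numerator and denominator.** For TEAEs, SAEs, fatal AEs and AEs leading to discontinuation of IP (DAEs), the on-treatment rate is ("number of participants reporting the TEAE) / (total time with participants at risk of TEAE"). The same formula is used over the on-study period for SAEs and fatal AEs.
- **Time at risk.** "The total period at risk for each participant will be the duration of the on-treatment and on-study periods as defined in Section 3.5.1".
- **Unit.** "Rates will be expressed in terms of events per 100 participant-years".
- **Purpose.** "key tables will include exposure-adjusted rates to account for any differences in follow-up if applicable".

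The overview table in the same section describes the figure differently, as an "exposure-adjusted rate of participants with at least 1 TEAE in any of the following categories". In the tables by SOC and PT the participant count is explained by the note that "multiple occurrences of an AE for a participant will only be counted once". Those tables also give the number of events.

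SAP 3.5.1 sets the period lengths. The on-treatment period runs from first dose to the earlier of the scheduled follow-up visit and last dose plus 12 weeks. For participants who enter the OLE, the double-blind part ends the day before the first OLE dose. Nothing in 3.5.1 shortens a participant's time because an event has occurred.

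**The concern.** There are two standard exposure-adjusted summaries. An event rate puts all events over all follow-up time. A first-event incidence rate puts participants with an event over time up to that first event, or to the end of the period if there is none. The SAP takes the numerator of the second, the denominator of the first, and the unit of the first.

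A reader who trusts the label will take the figure as an event rate. It cannot exceed that rate, because participants with an event never outnumber events. A reader who trusts the words *at risk* will take it as first-event incidence. It cannot exceed that either, because the denominator keeps the time after the first event.

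The figure is also meant to correct for unequal follow-up. Once a participant has had the event, each further week adds to the denominator and can add nothing to the numerator. For common events the figure therefore falls as follow-up lengthens, even when the underlying hazard is the same.

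**Working it through.** The documents contain no AE rate or expected incidence, so there is no figure of the plan's own to reproduce. The incidences and hazards below are assumptions shown over a range.

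**Inputs.** Double-blind period of 36 weeks (SAP 1.2.2) and 365.25 days per year (SAP 3.1.4), so T = 36 × 7 / 365.25 = 0.690 years. Assumed: constant hazard λ and, at first, the same T for everyone.

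**Formulas, per 100 participant-years.** With p the proportion who have the event:
- SAP figure: 100 × p / T
- First-event rate: 100 × λ = −100 × ln(1 − p) / T
- Shortfall of the SAP figure: 1 − p / (−ln(1 − p)), which does not depend on T

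| Assumed p | SAP figure | First-event rate | SAP figure low by |
|---|---|---|---|
| 2% | 2.9 | 2.9 | 1% |
| 5% | 7.2 | 7.4 | 2.5% |
| 10% | 14.5 | 15.3 | 5% |
| 20% | 29.0 | 32.3 | 10% |
| 50% | 72.5 | 100.5 | 28% |
| 80% | 116.0 | 233.3 | 50% |

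Under equal 36-week follow-up the SAP figure cannot exceed 100 / 0.690 = 144.9, however many events occur.

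**Read as an event rate.** Take Poisson events at 300 and 200 per 100 participant-years, a true ratio of 1.50. The formula prints 100 × (1 − e^(−3 × 0.690)) / 0.690 = 126.6 and 100 × (1 − e^(−2 × 0.690)) / 0.690 = 108.5, a ratio of 1.17.

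**Ratio between arms, equal follow-up.** T cancels, so the printed ratio is the risk ratio. With a hazard ratio of 1.5 it is [1 − (1 − p)^1.5] / p, where p is the placebo incidence: 1.29 at p = 50% and 1.14 at p = 80%. At low incidence the two measures agree: 2% vs 1% gives a risk ratio of 2.00 and a first-event rate ratio of 2.01.

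**Ratio between arms, unequal follow-up.** The SAP figure is 100 × (1 − e^(−λT)) / T in each arm.

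| Hazards per 100 participant-years | Follow-up, weeks | True ratio | Printed ratio |
|---|---|---|---|
| 200 vs 200 | 24 vs 36 | 1.00 | 130.8 / 108.5 = 1.21 |
| 200 vs 150 | 20 vs 36 | 1.33 | 1.49 |
| 200 vs 150 | 36 vs 20 | 1.33 | 0.95 |

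Some variation in follow-up is built into the design. An OLE entrant contributes about 36 weeks. A participant who has the Week 32 dose and does not enter the OLE contributes up to 32 + 12 = 44 weeks. At a hazard of 100, these lengths print 72.2 and 67.6, a ratio of 1.07 with no true difference.

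**The case against.** **The printed ratio is a legitimate quantity.** With equal follow-up it is the risk ratio. It looks pulled toward 1 only if the hazard ratio is taken as the target, and neither document makes it the target for safety. This stands. A reader might infer that the formula shrinks arm differences in general, but the documents do not support that. It is true of rate ratios for common AEs when follow-up is similar. With unequal follow-up the distortion can run either way and can create a difference.

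**The information is not lost.** Numbers and percentages of participants are shown in the overview, event counts are shown by SOC and PT, and SAP 4.2.9 makes safety descriptive. This also stands. A reader might infer that this rate is the main comparative safety summary, but the SAP does not say so. Rates accompany the counts and percentages and are qualified as applicable. No test, margin or stopping rule uses them.

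**Most rows are barely affected.** The SAP's threshold for a most-common TEAE is above 5%, where the shortfall begins at about 2.5%. Deaths are essentially untouched because follow-up ends at the event. For DAEs in the on-treatment period, the excess time is limited by the 12-week tail after the last dose. This limits the size of the problem and does not remove it.

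**Time at risk may have been meant to stop at the first event.** This does not stand. The sentence defining it ("The total period at risk for each participant will be the duration of the on-treatment and on-study periods") leaves no room for that reading, and SAP 3.5.1 does not supply the missing rule.

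**A first-event rate has its own assumption.** It summarises the hazard as one constant and also depends on length of follow-up if the hazard changes over time. That is fair, and is a reason to state the assumption.

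**Conclusion.** The point holds as an error of definition and labelling with limited numerical reach. The numerator, denominator and unit in SAP 4.2.9.1 do not belong to the same rate, and the result only partly makes the adjustment for follow-up that the section promises.

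Against a first-event rate, the figure is low by about 5% at 10% incidence, 28% at 50% and 50% at 80%. These sizes assume a constant hazard and, for the rates themselves, 36 weeks of follow-up; the incidences are illustrative. The practical effect is on the any-TEAE row and very common terms. For rare events and deaths it is negligible.

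Described as participants with at least one event per 100 participant-years of follow-up, the figure would be correctly named. It would still be an incomplete adjustment when follow-up differs between arms. Percentages, event counts and all hypothesis tests are unaffected.

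**What to change.** Amend SAP 4.2.9.1 so that each rate has a matching numerator, denominator and label.

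- **Participant-based rates:** stop each participant's time at the first event of that type, otherwise at the end of the period. Label the result *participants with an event per 100 participant-years at risk*.
- **Event rates:** divide the number of events by total time in the period and keep the events label.
- **Minimum change if the current formula is kept:** relabel it *participants with at least one event per 100 participant-years of follow-up*.

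The cost is SAP wording and minor reprogramming, since time at risk must be derived separately for each event type. No new data are needed. A table footnote should say that a first-event rate treats the hazard as constant.

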4.2.9.2 Clinical laboratory safety assessments

All protocol-specified continuous laboratory parameters will be summarized descriptively by absolute value at each visit by treatment group, together with the corresponding changes from baseline, separately for the double-blind period and the OLE period. All parameters will be summarized in SI units, except for blood eosinophil counts which will be summarized in both SI and conventional units. Results reported by the central laboratory in conventional units will be converted to SI units for reporting.

For continuous data, the summary statistics presented will be the n, mean, standard deviation, median, minimum value and maximum value.

Central laboratory reference ranges will be used for the identification of abnormalities, and a shift table will be produced for each laboratory parameter to display low, normal, and high values. The shift tables will present baseline and maximum/minimum on-treatment value, as applicable for each parameter and will include participants with both baseline and post-baseline data.

Shift plots showing each individual participant's laboratory value at baseline and at maximum/minimum post-baseline will be produced for each continuous laboratory variable. If any laboratory variables show any unusual features (high or low values or a general shift in the data points) at other time points, then shift plots of these data may be produced.

Data for participants who have treatment-emergent changes outside central laboratory reference ranges will be presented. This data presentation will include all visits for those participants.

Maximum post-baseline TBL elevations by maximum post-baseline ALT and AST will be presented, expressed as multiples of the upper limit of normal (ULN). Total bilirubin will be presented in multiples of the following ULN: ≤ 1.5 , $>1.5-2$, >2 . AST and ALT will be presented in multiples of the following ULN: ≤ 1 , $>1-3$, $>3-5$, $>5-10$, >10 .

Maximum post-baseline TBL will be presented (<2 and $\geq 2 \times$ ULN) and plotted against maximum post-baseline ALT (<3 , $\geq 3-5$, $\geq 5-10$, and $\geq 10 \times$ ULN), expressed as multiples of ULN. This will be repeated to show maximum post-baseline TBL against maximum post-baseline AST.

Data for participants who meet the biochemical criteria for Hy's law (ALT or AST $\geq 3 \times$ ULN and TBL $\geq 2 \times$ ULN) will be presented, which will include all visits for this subset of participants. A line plot of liver biochemistry test results (including ALP, ALT, AST, TBL, and GGT) over time will also be presented for this subset of participants. For all participants who meet the biochemical criteria for confirmed Hy's law, a SAE narrative will be produced.

For urinalysis data, a shift table will be generated to present changes from baseline to maximum/minimum post-baseline value, displaying normal and abnormal values for selected parameters and will include participants with both baseline and post-baseline data.

Any data outside the central laboratory reference ranges will be explicitly noted on the listings.

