Week (Wk)		0	2	4	6	8	12	16	20	24	28	32	36	40-72	60	From Week 76					
Visit window (days)	(Target 0-4 days)	±3	±3	±3	±3	±3	±3	±3	±3	±3	±3	±3	±3	±7	±7	±7	±7				
HIV express test	X																				Section 8.2.4.2
Hepatitis B and C serology m	X																				Section 8.2.4.2
Urine pregnancy test in FOCBP n	X						X			X			X b								Section 8.2.4.1
Confirmatory BP diagnostic testing	X o																				Section 5.1
Central Laboratory Assessments																					
Hematology and Clinical chemistry	X m						X						X		X		X	X	X p		Section 8.2.4
Hepatitis/HIV screening	X																				Section 8.2.4.2
HbA1c		X					X			X			X		X	X q	X q				Section 8.2.4

**Table 2** Schedule of Activities

Study period	Screening	Double-blind treatment period													OLE			IPD/EOT c	FU (12 wks after last dose of IP)	UNS d	Details in CSP section
		V2	V3	V4	V5	V6	V7	V8	V9	V10	V11	V12	V13/ EOT a	Every 4 wks (V14 to V22) b	V19	Every 12 weeks (From V23)					
Visit	V1																				
Week (Wk)		0	2	4	6	8	12	16	20	24	28	32	36	40-72	60	From Week 76					
Visit window (days)	(Target 0-4 days)	±3	±3	±3	±3	±3	±3	±3	±3	±3	±3	±3	±3	±7	±7	±7	±7				
FSH	X																		Section 8.2.4.1		
PK sample		X	X	X	X t		X		X			X		X		X		X s	Section 8.5.1		
ADA/nAb		X		X t		X		X			X		X		X		X s	Section 8.5.2			
CCI		X																	Section 8.7.1		
Exploratory Biomarkers																					
Whole blood (including CCI [REDACTED] [REDACTED] and eosinophil count), serum and plasma for biomarkers		X	X t		X					X			X		X		X s	Section 8.6.1.1			

**Table 2** Schedule of Activities

Study period	Screening	Double-blind treatment period													OLE			IPD/EOT c	FU (12 wks after last dose of IP)	UNS d	Details in CSP section
		V2	V3	V4	V5	V6	V7	V8	V9	V10	V11	V12	V13/ EOT a	Every 4 wks (V14 to V22) b	V19	Every 12 weeks (From V23)					
Visit	V1																				
Week (Wk)		0	2	4	6	8	12	16	20	24	28	32	36	40-72	60	From Week 76					
Visit window (days)	(Target 0-4 days)	±3	±3	±3	±3	±3	±3	±3	±3	±3	±3	±3	±3	±7	±7	±7	±7				
Skin biopsy for histology/ immunohistochemistry and CCI	X v													X						Section 8.6.1.2	

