- k Complete physical examination includes an assessment of the following: height and weight, general appearance, skin, head and neck (including eyes, ears, nose, mouth, and throat), lymph nodes, abdomen, musculoskeletal (including spine and extremities), cardiovascular, respiratory, and neurological systems.
- l Brief physical examination includes assessment of the following: weight, general appearance, skin, abdomen, cardiovascular, and respiratory system. For the brief physical examination, only information on whether the assessment was performed or not is to be recorded. Weight measurements will be performed in light clothing and without shoes and will be recorded in kilograms.
- m Testing to be conducted at local laboratory, confirmation testing to be conducted by a central laboratory.
- n A positive urine pregnancy test result must be confirmed with a serum pregnancy test.
- o Confirmatory local testing is required for those who do not have a confirmed BP diagnosis.
- p An unscheduled hematology and clinical chemistry should be performed if the visit is for relapse.
- q If not conducted in the previous 3 months.
- r Samples will be taken only at one time point, ie, at the visit when disease control has been achieved.
- s Samples will be taken at an unscheduled visit if the visit is for relapse.
- t Blood biomarkers will be collected only at one of the time points between Visits 4 and 6; ie, only at the visit that disease control has been achieved and before steroid taper is commenced.
- u Skin biopsies will be taken from peri-lesional skin for histopathology and CCI [REDACTED] research.
- v For participants without a confirmed diagnosis, no biopsy for CCI [REDACTED] is collected. In these participants, the biopsy will be for inclusion criteria confirmation at the local lab and immunohistochemistry for exploratory research.
- w Benralizumab administration only; for participants who continue the study in the open-label extension.

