## BP Relapse

In the event of a suspected BP relapse (see [Table 6](#) for definition), the participant should attend an unscheduled visit. A BPDAI evaluation will be conducted at the time of the relapse, or as soon as possible afterwards.

Investigators will be required to record details pertaining to each relapse event in the eCRF from baseline (Visit 2) until IPD visit/end of treatment and follow-up visit. Details should include the BPDAI activity and pruritus score and the required intervention(s), eg, OCS dose increase, the OCS dose at the time of relapse, addition of immunosuppressive therapy or requirement for hospitalization. Participants who require the addition of OCS after taper or an increase in the dose of OCS will be defined as having a relapse.

The management of participants who relapse will be according to standard of care. See [Section 6.5.1](#) for further details. The participant's relapse is managed with the addition of OCS and tapering should be recommended as soon as the relapse has been appropriately controlled as per current guidelines ([Feliciani et al 2015](#)). In case of a relapse during steroid tapering, the OCS dose may be increased to the previous dosage that symptoms were controlled. For recurrent relapses the OCS dosing regimen and tapering schedule will be at the Investigator's discretion. If the participant requires therapy other than OCS (eg, immunosuppressants), the study treatment may need to be discontinued but this should be discussed with the study physician prior to decision making. In the event that discontinuation of IP is required, the participant will still be asked to continue with the study assessments until the end of the double-blind period at Week 36. For relapse during OLE, the use of topical and/or oral corticosteroids and the schedule of taper will be at the discretion of the Investigator; however, it is recommended to follow the protocol taper schedule. The goal of therapy will be to taper off steroids to benralizumab monotherapy as soon as clinically indicated. In the event that the Investigator will need to control relapse with an immunosuppressant in the OLE, the participant will be withdrawn from the study and will not receive further benralizumab therapy. Participants may additionally be asked to allow future contact to provide follow-up clinical details regarding their health and information on disease state.

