#### **9.4.3.3 Clinical Safety Laboratory Assessments**

Laboratory data for hematology and clinical chemistry will be summarized. The frequency of changes with respect to normal ranges between baseline and each post-treatment time point will be tabulated. Frequencies of clinically noteworthy values (defined in the SAP) occurring during the clinical study will also be given.

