Adjusted defined window visit*	Scheduled study day	Maximum windows
Week 40	281	Visit 13 date or 280 whatever is earlier < Study day \leq 295
Week 44	309	$296 \leq$ Study day \leq 323
Week 48	337	$324 \leq$ Study day \leq 351
Week 52	365	$352 \leq$ Study day \leq 379
Week 56	393	$380 \leq$ Study day \leq 407
Week 60	421	$408 \leq$ Study day \leq 435
Week 64	449	$436 \leq$ Study day \leq 463
Week 68	477	$464 \leq$ Study day \leq 491
Week 72	505	$492 \leq$ Study day \leq 519
Week 76	533	$520 \leq$ Study day \leq 575
Week 88	617	$576 \leq$ Study day \leq 659
Week 100	701	$660 \leq$ Study day \leq 743
Every 12 weeks	Scheduled Study Day	$744 \leq$ Study day \leq Scheduled Study Day + 42

If multiple assessments are recorded within a single adjusted visit window, please refer to the rules below.

If there are 2 or more observations within the same visit window, then the non-missing observation closest to the scheduled study day will be used in the analysis.

If 2 observations are equidistant from the scheduled study day, then the non-missing observation with the earlier collection date will be used in the analysis.

If 2 observations are collected on the same day then the non-missing observation with the earlier collection time will be included in the analysis.

If two or more values are located on the same side of the target day at the same date and time and are the closest to the target day, the mean of the values will be included in the analysis.

Note: in summaries of extreme values all on-treatment post baseline values collected are used including those collected at unscheduled visits regardless of whether the value is closest to the target visit day.

If a visit window does not contain any observations, then the data will remain missing.

For endpoints which are not collected at every visit, the above rules will be applied to derive adjusted analysis-defined visit windows based on the protocol defined visit schedule for that endpoint. Similarly, for laboratory parameters not collected at every visit.

When converting the number of days to other units, the following conversion factors will be used: 1 week = 7 days; 1 year = 365.25 days.

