3.5 Safety outcome variables

Safety and tolerability will be evaluated in terms of: reported AEs (including serious adverse events [SAEs]), clinical laboratory assessments, vital signs, physical examination and 12-lead electrocardiogram (ECG).

All safety measurements will use all available data for analyses, including data from unscheduled visits and repeated measurements.

Change from baseline to each post-treatment time point where scheduled assessments were made will be calculated for relevant measurements. Safety data will be summarized by means of descriptive statistics and qualitative summaries.

The handling of partial/missing dates for AEs is detailed in Appendix 8.3. Duration of AEs will not be calculated using imputed dates and will instead be set to missing. No other safety data will be imputed.

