3.5.2 Clinical laboratory variables

Blood and urine samples for determination of clinical chemistry, haematology and urinalysis parameters will be taken at the times detailed in the CSP Table 2 during the double-blind and OLE periods. The parameters outlined in the CSP Table 7 will be collected. Local laboratory results will not be included in the analysis.

In summaries, figures, and listings, laboratory results and normal ranges will be presented in System International (SI) units. Eosinophil data will be presented in both SI and conventional units (cells/ μ L) in summaries.

Changes in haematology and clinical chemistry variables between baseline and each post-baseline assessment will be calculated. For values recorded with a leading greater than or less than (‘>’, ‘<’) symbol, the reported numeric value will be used for analysis and the value with the symbol will be included in the listings, unless otherwise specified. For example, a value of <0.01 will be analysed as 0.01 and listed as <0.01.

Absolute values will be compared to the relevant reference range and classified as low (below range), normal (within range or on limits) or high (above range). The central reference ranges will be used for laboratory variables. All absolute values falling outside the reference ranges will be flagged.

Maximum or minimum value post-baseline will be calculated over the entire post-baseline period, including the post-treatment period. The maximum or minimum value post-baseline will be calculated over the double-blind period for all participants and during the OLE period for the participants who are included in the OLE period.

For the liver function tests aspartate aminotransferase (AST), alanine aminotransferase (ALT), alkaline phosphatase (ALP), gamma-GT (GGT) and total bilirubin (TBL), the multiple of the central laboratory upper limit of the normal (ULN) range will be calculated for each data point.

$$\text{Multiple} = \text{Value} / \text{ULN}$$

That is, if the ALT value was 72 IU/L (ULN=36) then the multiple would be 2.

Participants who meet any of the following criteria at any point during the study will be flagged:

AST \geq 3x ULN

ALT \geq 3x ULN

TBL \geq 2xULN

Urinalysis data with qualitative results will be categorized as negative (0), positive (+), or strongly positive (++, +++, or >++) at each timepoint.

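### SAP laboratory shift tables use only the most extreme value, relapse-triggered draws included, and the protocol's shift table by time point is dropped without being declared

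*SAP*

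**What the plan says.** **Protocol commitment.** Protocol 9.4.3.3: "The frequency of changes with respect to normal ranges between baseline and each post-treatment time point will be tabulated".

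**SAP replacement.** SAP 4.2.9.2 defines the low/normal/high shift tables in one way: "The shift tables will present baseline and maximum/minimum on-treatment value". The section has no shift table by visit. By visit it gives descriptive absolute values and changes from baseline.

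**Which values can be the extreme.** SAP 3.1.4 notes that "in summaries of extreme values all on-treatment post baseline values collected are used including those collected at unscheduled visits". SAP 3.5 has the same rule for safety data generally: "including data from unscheduled visits and repeated measurements". SAP 3.5.2 adds that "Local laboratory results will not be included in the analysis", so only central results count.

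**When extra draws occur.** Under the protocol's BP Relapse heading, on suspected relapse "the participant should attend an unscheduled visit". Footnote p to the Schedule of Activities (Protocol Table 2) then says: "An unscheduled hematology and clinical chemistry should be performed if the visit is for relapse". That footnote sits in the unscheduled-visit column of the central-laboratory row, so these draws enter the analysis.

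**Declaration.** SAP Section 1 says that changes from the protocol will be described in Section 6. Section 6 has four items: the open-label extension (OLE) analysis set, restricted medications, missing disease-state assessments, and the BPDAI ANCOVA covariate. None concerns laboratory shifts.

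**The concern.** There are two linked problems.

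The first needs no assumption. A safety table specified in the protocol has no counterpart in the SAP, and the departure is not recorded where the SAP says it would be.

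The second is conditional. A shift to the most extreme value becomes more likely the more often a participant is sampled. Here the number of samples depends partly on relapse. Freedom from relapse is the first key secondary endpoint, and Protocol 2.3 expects fewer relapses on benralizumab. If that expectation holds, placebo participants would on average have more central draws, and the display of abnormal laboratory values by arm would tilt slightly against placebo for reasons unrelated to drug toxicity. A table with one scheduled value per participant at each time point does not depend on extra draws in this way.

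**Working it through.** The documents give no figure for this effect, so there is none to reproduce. The check estimates how large it could be.

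**Inputs**
- Scheduled central hematology and chemistry draws after baseline in the double-blind period: 2 (Weeks 12 and 36). This is read from column positions in Protocol Table 2 as extracted.
- Extra draws: at most one per relapser (assumption).
- Placebo relapse: 67%, from the 33% relapse-free on placebo in the mepolizumab trial cited in Protocol 9.2 and SAP 1.3. Using it here is an assumption.
- Benralizumab relapse: not given. Assumed 37-40%, with 20%, 50% and 67% as further values.
- Chance that one draw is out of range with no drug effect: not given. Assumed 5% (2.5% on each side of a 95% reference range).
- Within-person correlation: not given. Values of 0, 0.5 and 0.7 were used.

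**Independent draws.** The chance of at least one out-of-range value in k draws is 1 − (1 − p)^k.
- k = 2: 1 − 0.95² = 9.75%.
- k = 3: 1 − 0.95³ = 14.26%.
- One relapse draw therefore adds 4.51 points for a participant who has it.

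The expected rate in an arm with relapse proportion r is 9.75% + r × 4.51%.
- Placebo, r = 0.67: 12.8%.
- Benralizumab, r = 0.40: 11.6%. Gap 0.27 × 4.51 = 1.2 points.
- Benralizumab, r = 0.37: 11.4%. Gap 0.30 × 4.51 = 1.4 points.

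**Correlated draws.** Values were simulated from a normal model for participants in range at baseline. The rates for two and three draws feed the same mixture.

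| Correlation | 2 draws | 3 draws | Added by one draw (points) | Gap, 67% vs 40% (points) | Gap, 67% vs 37% (points) |
|---|---|---|---|---|---|
| 0 | 9.75% | 14.26% | 4.51 | 1.2 | 1.4 |
| 0.5 | 7.94% | 11.14% | 3.20 | 0.9 | 1.0 |
| 0.7 | 6.22% | 8.44% | 2.22 | 0.6 | 0.7 |

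**Range over benralizumab relapse rates.** Across the three correlations the gap is 1.0-2.1 points at 20% relapse and 0.4-0.8 points at 50%. At 67%, equal to placebo, it is zero.

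**Participants.** The SAP plans 50 per arm. A gap of 1.4 points is 0.7 of a participant per parameter, and 0.7 points is about 0.35.

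**Under the protocol's table.** With one scheduled value per participant at a time point, the expected rate with no drug effect is the same in both arms whatever their relapse rates: 5% with independent draws, about 4.3% at correlation 0.5 and 3.5% at 0.7. The gap due to extra draws is zero.

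**The case against.** The strongest reply is that the worst on-treatment value is a deliberately sensitive screen, that the protocol leaves technical detail to the SAP, and that safety is reported descriptively, so no formal test can be biased. Protocol 9.4.3.3 itself also plans an any-time summary, of clinically noteworthy values. All of this stands, and it is why the extreme-value tables should stay. It does not explain why the by-time-point table is gone or why Section 6 is silent.

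The extra-draw assumption is also an upper one for a single relapse. A relapse found at a scheduled visit may add no draw. The SAP's relapse endpoint counts withdrawal, restricted medication and missing data as not relapse-free, and none of these triggers footnote p. Repeated relapses would work the other way and were not modelled. The same schedule row has discontinuation and follow-up draws that the count of two leaves out. Starting from three draws, the step is 18.55% − 14.26% = 4.29 points, so little changes.

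Some stronger readings are tempting but not supported:
- A reader might infer that placebo will show more abnormal values, or that a benralizumab signal will be hidden. The first depends on unequal relapse rates, which are not known. The second overlooks outputs that remain: by-visit values and changes by arm, all-visit data for participants with treatment-emergent out-of-range changes, liver tables with Hy's law data, and flagged listings.
- A reader might take 67-80% as the placebo relapse range. The 80% belongs to the mepolizumab arm of the cited trial.
- A reader might suppose a large gap. If 10% of scheduled draws and 30% of relapse draws were abnormal, it would be 0.27 × 0.81 × 0.30 = 6.6 points at 67% versus 40% relapse. Nothing in the documents supports the 30%, and part of such an excess could be a real effect of active disease or higher steroid dose.
- A reader might expect the by-time-point table to guarantee equal ascertainment. Withdrawal still affects it, and the windowing in SAP 3.1.4 could let a relapse draw fill a missing scheduled value unless the table is limited to scheduled samples.

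**Conclusion.** The concern holds as a minor one. The missing table and the undeclared change are established from the text alone. The dependence of sampling on relapse is also in the text, but its effect on the arm comparison is conditional and small: 1.2-1.4 points per parameter with independent draws and 0.6-0.7 at correlation 0.7, under the assumptions of 5% abnormal per draw, two scheduled draws, at most one extra draw per relapser, and 67% versus 37-40% relapse. At 10% abnormal per draw and independence the step is 0.81 × 0.10 = 8.1 points and the gap 2.2-2.4 points.

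The by-visit means and standard deviations do not fill the hole, because they do not show how many participants moved out of range. Further shift plots at other time points are only optional.

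The SAP also disagrees with itself on the period covered. Section 4.2.9.2 limits the shift-table extremes to on-treatment values, while Section 3.5.2 takes maxima and minima over the whole period after baseline, post-treatment included.

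**What to change.** In SAP 4.2.9.2:
1. Restore the shift table from baseline to each scheduled time point, using scheduled central-laboratory values only, as the between-arm display. SAP 3.5.2 already classifies each value as low, normal or high, so no new derivation or data are needed.
2. Keep the maximum/minimum tables with all values for signal detection. Label them as including relapse-triggered samples, and preferably show the number of draws per arm.
3. State one period for the maximum and minimum, and align Sections 3.5.2 and 4.2.9.2 with it.

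If the sponsor prefers extremes only, Section 6 should list that as a change from Protocol 9.4.3.3.

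The cost is one extra standard table per parameter.
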